11.1.3 Expectedness

Adverse events can be 'Expected' or 'Unexpected.'

11.1.3.1 Expected adverse event

Expected adverse events are those that have been previously identified as resulting from administration of the agent. For the purposes of this study, an adverse event is considered expected when it appears in the current adverse event list, the Investigator's Brochure, the package insert or is included in the informed consent document as a potential risk.

Refer to Section 7 for a listing of expected adverse events associated with the study agent(s).

11.1.3.2 Unexpected adverse event

For the purposes of this study, an adverse event is considered unexpected when it varies in nature, intensity or frequency from information provided in the current adverse event list, the Investigator's Brochure, the package insert or when it is not included in the informed consent document as a potential risk.

11.1.4 Attribution

Attribution is the relationship between an adverse event or serious adverse event and the study treatment. Attribution will be assigned as follows:

- Related – There is reasonable evidence that the AE is related to the study treatment.
- Unrelated - The AE is clearly NOT related to the study treatment.

11.2 Procedures for AE and SAE Recording and Reporting

Participating investigators will assess the occurrence of AEs and SAEs at all participant evaluation time points during the study.

CONFIDENTIAL

This document is confidential. Do not disclose or use except as authorized.

All AEs and SAEs whether reported by the participant, discovered during questioning, directly observed, or detected by physical examination, laboratory test or other means, will be recorded in the participant's medical record and on the appropriate study-specific case report forms.

The descriptions and grading scales found in the revised NCI Common Terminology Criteria for Adverse Events (CTCAE) version 4.0 will be utilized for AE reporting. All appropriate treatment areas should have access to a copy of the CTCAE version 4.0. A copy of the CTCAE version 4.0 can be downloaded from the CTEP website at:

http://ctep.cancer.gov/protocolDevelopment/electronic_applications/ctc.htm.

11.3 Reporting Requirements

Each participating investigator is required to abide by the reporting requirements. The study must be conducted in compliance with FDA regulations, local safety reporting requirements, and reporting requirements of the principal investigator.

Each investigative site will be responsible to report SAEs that occur at that institution to their respective IRB. It is the responsibility of each participating investigator to report serious adverse events to the PI of this study, [name], and/or others as described below.

11.4 Reporting to the Study Sponsor

11.4.1 Serious Adverse Event Reporting

All serious adverse events that occur after the initial dose of study treatment, during treatment, or within 30 days of the last dose of treatment must be reported to the Principal Investigator, [name], on the local institutional SAE form. This includes events meeting the criteria outlined in Section 11.1.2, as well as the following:

- Grade 2 (moderate) and Grade 3 (severe) Events – Only events that are unexpected and related with the intervention.
- All Grade 4 (life-threatening or disabling) Events – Unless expected AND specifically listed in the protocol as not requiring reporting.
- All Grade 5 (fatal) Events – When the participant is enrolled and actively participating in the trial OR when the event occurs within 30 days of the last study intervention.

Note: If the participant is in long term follow up, report the death at the time of continuing review.

CONFIDENTIAL

This document is confidential. Do not disclose or use except as authorized.

Participating investigators must report each serious adverse event to the Principal Investigator [name] within 24 hours of learning of the occurrence. In the event that the participating investigator does not become aware of the serious adverse event immediately (e.g., participant sought treatment elsewhere), the participating investigator is to report the event within 24 hours after learning of it and document the time of his or her first awareness of the adverse event. Report serious adverse events by telephone, email or facsimile to:

[name]
c/o
[name] [contact]

[name]
[name]
[name]
[contact]

The participating investigator must provide follow-up information on the serious adverse event as soon as possible. Follow-up information should describe whether the event has resolved or continues, if and how the event was treated, and whether the participant will continue or discontinue study participation.

11.4.2 Non-Serious Adverse Event Reporting

Non-serious adverse events will be reported to the Principal Investigator [name] on the toxicity Case Report Forms.

11.5 Reporting to the Institutional Review Board (IRB)

Other investigative sites should report serious adverse events to their respective IRB according to the local IRB's policies and procedures in reporting adverse events. A copy of the submitted institutional SAE form should be forwarded to:

[name]
c/o [name] [contact]

[name]
[name]
[name]

The Principal Investigator [name] will submit SAE reports from outside institutions, if applicable, to the Cornell IRB per their policies and procedures in reporting adverse events.

CONFIDENTIAL

This document is confidential. Do not disclose or use except as authorized.

11.6 Reporting to the Food and Drug Administration (FDA)

The Principal Investigator [name], as holder of the IND, will be responsible for all communication with the FDA. [name] will report to the FDA, regardless of the site of occurrence, any adverse event that is serious, unexpected and related to the study treatment (Suspected Unexpected Serious Adverse Reactions or SUSARs) according the regulatory-defined timelines (7-day or 15-day reports). [name] will copy Astex pharmaceuticals (SGI-110 manufacturer) on any such reports.

In accordance with the regulation 21 CFR § 312.33, the IND Sponsor shall within 60 days of the anniversary date that the IND went into effect submit a brief report of the adverse events and progress of the investigation. All IND annual reports will be submitted to the FDA by the IND Sponsor.

Events will be reported to the FDA using Form FDA 3500A (Mandatory Reporting Form for investigational agents) or FDA Form 3500 (Voluntary Reporting Form for commercial agents). Forms are available at <http://www.fda.gov/medwatch/getforms.htm>.

7 Calendar-Day Telephone or Fax Report:

The IND Sponsor is required to notify the FDA of any fatal or life-threatening adverse event that is unexpected and assessed by the investigator to be possibly related to the investigational agent. Such reports are to be telephoned or faxed ([name]) to the FDA within 7 calendar days of first learning of the event.

15 Calendar-Day Written Report:

The IND Sponsor is required to notify the FDA of any serious adverse event that is unexpected and possibly related to the investigational agent in a written IND Safety Report.

Written IND Safety Reports should include an Analysis of Similar Events in accordance with regulation 21 CFR § 312.32. All safety reports previously filed with the IND concerning similar events should be analyzed. The new report should contain comments on the significance of the new event in light of the previous, similar reports. Written IND safety reports with Analysis of Similar Events are to be submitted to the FDA within 15 calendar days of first learning of the event.

11.7 Reporting to Hospital Risk Management

Participating investigators will report to their local Risk Management office any subject safety reports or sentinel events that require reporting according to institutional policy.

11.8 Monitoring of Adverse Events and Period of Observation

All adverse events, both serious and non-serious, and deaths that are encountered from initiation of study intervention, throughout the study, and within 30 days of the last study intervention should be followed to their resolution, or until the participating

CONFIDENTIAL

This document is confidential. Do not disclose or use except as authorized.

investigator assesses them as stable, or the participating investigator determines the event to be irreversible, or the participant is lost to follow-up. The presence and resolution of AEs and SAEs (with dates) should be documented on the appropriate case report form and recorded in the participant's medical record to facilitate source data verification.

For some SAEs, the study sponsor or designee may follow-up by telephone, fax, and/or monitoring visit to obtain additional case details deemed necessary to appropriately evaluate the SAE report (e.g., hospital discharge summary, consultant report, or autopsy report).

Participants should be instructed to report any serious post-study event(s) that might reasonably be related to participation in this study. Participating investigators should notify the Overall Principal Investigator and their respective IRB of any unanticipated death or adverse event occurring after a participant has discontinued or terminated study participation that may reasonably be related to the study.

12. DATA AND SAFETY MONITORING

12.1 Data Reporting

12.1.1 Data monitoring of this protocol will occur on a regular basis with the frequency dependent on the rate of subject accrual and the progress of the study. The protocol will be monitored internally at Cornell by [name] and externally by the Cornell CRO QA Office and the Coordinating Center in accordance with the Cornell Data Safety Monitoring Plan. All trial monitoring and reporting will be done through the Safety Monitoring Committee (SMC) at Cornell. Authorized representatives of the Coordinating Center may visit the site to perform audits or inspections, including source data verification. The purpose of these audits or inspections is to systematically and independently examine all trial-related activities and documents to determine whether these activities were conducted and data were recorded, analyzed, and accurately reported according to the protocol, Good Clinical Practice (GCP), and any applicable regulatory requirements.

12.1.2 [name] will be holding the IND for this study. She will comply with all regulated reporting requirements to the FDA.

Weill Cornell Medical College requires that all research approved by the WCMC IRB include an appropriate plan for the monitoring of data to ensure the safety of human subjects. Research supported by Federal agencies will be monitored according to all regulations and guidelines of the relevant Federal agency. The WCMC Data and Safety Monitoring Board (DSMB) will review the IRB approved protocol, informed consent documents, and data and safety monitoring plan prior to study initiation. After the first fifteen patients have been treated and observed for 28 days, the DSMB will perform an initial safety analysis. After the initial safety analysis period, the DSMB will review the cumulative study data semiannually to evaluate safety, efficacy, study conduct, and scientific validity and integrity of the trial. Due to the nature of the underlying diseases of the subjects on this study and the prolonged duration of therapy that

CONFIDENTIAL

This document is confidential. Do not disclose or use except as authorized.

may be required in order to observe clinical benefit with the proposed treatment, there will be no assessment of efficacy until at least 25 patients have been treated for at least 4 cycles of therapy. If, at that point, there are fewer than 10% responses, as defined in the protocol, the study will be stopped for futility. The WCMC DSMB may also convene as needed if stopping criteria are met or other safety issues arise that the Principal Investigator and/or IRB would like the WCMC DSMB to address.

Stopping criteria also include:

- The early death of more than three of the first ten subjects, as defined by death within 28 days of beginning therapy.
- If there is an unacceptable rate of Grade 4 toxicities, as judged by the investigation team, study sponsor, or the WCMC DSMB.

The study PI will submit all written DSMB recommendations to the IRB upon receipt.

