2.4 Study disease: MPN

Philadelphia chromosome negative Myeloproliferative Neoplasms (PHN-MPN) comprise a group of myeloid neoplasms with varying clinical, morphologic and laboratory features and a wide range of survival. According to 2008 World Health Organization (WHO) classification, the MDS/MPN overlap syndromes include chronic myelomonocytic leukemia (CMML), atypical chronic myeloid leukemia (aCML), juvenile myelomonocytic leukemia (JMML) and myelodysplastic/myeloproliferative neoplasm unclassifiable (MDS/MPN-U). In a recent retrospective study from MD Anderson Cancer Center, the median survival of patients with a

CONFIDENTIAL

This document is confidential. Do not disclose or use except as authorized.

diagnosis of MDS/MPN unclassifiable was 12.4 months[3] . There is no effective therapy for PHN-MPN and this represents an unmet medical need.

The MDS/MPN overlap syndromes can present with a wide range of hematological and clinical manifestations and individual patients may exhibit a combination of features characteristic of both MDS and MPN. For example, while transfusion-dependent anemia is generally present, other hematological laboratory abnormalities can range from leukopenia to leukocytosis and from thrombocytopenia to thrombocytosis. Unlike with MDS, significant splenomegaly is often present in patients with PHN-MPN. Also, patients may have a constellation of constitutional findings, including fatigue, weight loss, anorexia, night sweats and other unpleasant symptoms that lead generally to poor quality of life. Thus, while improving overall survival is a critical goal of therapy, effective therapy for this group of patients will include also agents that can be demonstrated to improve as many of the disease-related clinical issues as possible.

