This is a phase II trial with 50 patients in the study arm; a 95% confidence interval for the hematological response rate can be constructed to be within $\pm 12.0\%$ of the observed response rate. This calculation assumes a hematological response rate of 25%. The primary endpoint is the hematological response proportion, as measured by any one or more of the following response assessments: IWG-MDS, IWG-MF criteria or MF-SAF scores. Based on historical data, the hematological response proportion based on standard therapies is approximately 10%. Sample size recommendations for the current design are determined according to A'Hern's exact single-stage phase II design (A'Hern, RP, 2001). We project a hematological response proportion of 10%, below which the regimen will be unacceptable, and a hematological response proportion of 25%, above which the regimen will be considered worthy of further exploration. The null hypothesis that the hematological response proportion is less than or equal to 10% will be tested against the alternative hypothesis that the hematological response proportion is greater than or equal to 25%. The sample size computations were performed assuming a 5% level of significance and 85% power. Patients will be continuously accrued throughout the study up to a maximum of 47 patients. The new regimen will be declared effective and worthy of further testing if 9 or more patients respond among the 47 patients entered into the study. This exact single-stage design yields a ≥ 0.85 probability of a positive result if the true hematological response proportion is $\geq 25\%$. It yields a ≥ 0.95 probability of a negative result if the true hematological response proportion is $\leq 10\%$. A one-sided 95% confidence interval constructed around the expected hematological response proportion of 25% will extend 10.4% from the observed hematological response proportion. Assuming that approximately 5% of patients will be unevaluable/ineligible, we anticipate that a total of 50 patients will be enrolled in the study (Reference: A'Hern AP. Sample size tables for exact single-stage phase II designs. Statistics in Medicine 2001;20:859-866.)

Analysis Plan:

CONFIDENTIAL

This document is confidential. Do not disclose or use except as authorized.

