14.2 Reporting and Exclusions

14.2.1 Evaluation of toxicity. All participants will be evaluable for toxicity from the time of their first treatment.

14.2.2 Evaluation of response. All participants included in the study must be assessed for response to treatment. Each participant should be assigned one of the following categories: 1) complete response, 2) partial response, 3) stable disease, 4) progressive disease, 5) early death from malignant disease, 6) early death from toxicity, 7) early death because of other cause, or 9) unknown (not assessable, insufficient data). By arbitrary convention, category 9 usually designates the "unknown" status of any type of data in a clinical database.

CONFIDENTIAL

This document is confidential. Do not disclose or use except as authorized.

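### The futility look is timed by patients who complete 4 cycles, so early stoppers do not advance it and it comes later the more patients stop early

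*Combined protocol and SAP*

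**What the plan says.** Section 12.1.2 states that "there will be no assessment of efficacy until at least 25 patients have been treated for at least 4 cycles of therapy". The rule follows directly: "If, at that point, there are fewer than 10% responses, as defined in the protocol, the study will be stopped for futility". The reason given is that benefit may need prolonged treatment to appear. No minimum number enrolled, calendar date or other backstop is attached, and the denominator of the 10% is not stated.

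The same section times its safety look differently: "After the first fifteen patients have been treated and observed for 28 days, the DSMB will perform an initial safety analysis". That trigger does not depend on how many cycles a patient completes. After it, "the DSMB will review the cumulative study data semiannually to evaluate safety, efficacy, study conduct", with no futility rule attached.

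Section 14.1 sets a single-stage design and says "Patients will be continuously accrued throughout the study up to a maximum of 47 patients", with 50 to be enrolled after allowing for 5% unevaluable or ineligible. No pause for the look is described. Section 14.2.2 says "All participants included in the study must be assessed for response to treatment", and its categories include progressive disease, three kinds of early death, and unknown.

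**The concern.** A futility stop exists to limit the number of patients given a drug that is not working. Here its timing depends on how many patients stay on treatment. Someone who dies, stops for toxicity, withdraws, or progresses and comes off treatment before completing 4 cycles is not counted towards the 25, although most such patients are already evidence about efficacy. The look is therefore latest when early failure is most common, which is when it would be most useful.

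The stated reason for waiting covers patients still on treatment, who may yet respond. It does not cover patients who have permanently stopped. At stake is the number of patients treated before an ineffective drug can be recognised, and in the extreme case whether the look happens before enrolment is complete.

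**Working it through.** **1. The plan's own design.** Inputs from Section 14.1: null rate 10%, target rate 25%, 5% one-sided significance, 85% power, success at 9 or more responders in 47.
- P(X ≥ 9 | n = 47, p = 0.10) = 0.041
- P(X ≥ 9 | n = 47, p = 0.25) = 0.865
- 47 is the smallest n that meets both limits, and 47 / 0.95 = 49.5, which rounds up to 50. The stated figures reproduce.

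**2. When the look falls as written.** Let r be the fraction of treated patients who reach 4 cycles. The documents do not give r, so a range is assumed. The expected number treated to obtain 25 qualifiers is 25 / r. The probability that 25 qualifiers ever accrue among N patients is P(Bin(N, r) ≥ 25).

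| Assumed r | 25 / r | Beyond 25 | P(look), N = 50 | P(look), N = 47 |
|---|---|---|---|---|
| 0.8 | 31.3 | 6.3 | 1.00 | 1.00 |
| 0.7 | 35.7 | 10.7 | 0.999 | 0.995 |
| 0.6 | 41.7 | 16.7 | 0.94 | 0.86 |
| 0.55 | 45.5 | 20.5 | 0.80 | 0.66 |
| 0.5 | 50.0 | 25.0 | 0.56 | 0.39 |

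The second column is a lower bound on enrolment at the look. Patients also enter during the roughly 4 × 28 = 112 days that the 25th qualifier needs. The accrual rate is not given, so that overrun cannot be sized.

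**3. What the documents offer as an anchor for r.** Section 2.4 cites a retrospective series in which median survival of patients with a "diagnosis of MDS/MPN unclassifiable was 12.4 months". Assuming exponential survival, 12.4 months × 30.44 days = 377 days, and survival at 112 days is 0.5^(112/377) = 0.81. This allows for death only and for one of several eligible diagnoses. Progression, toxicity and withdrawal would lower r; the other diagnoses could move it either way.

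**4. The look with a fixed set of 25.** Suppose the look is taken on the first 25 patients to start treatment, all in the denominator. Fewer than 10% of 25 means fewer than 2.5, that is 2 or fewer responders.
- P(X ≤ 2 | n = 25) = 0.87 at a true rate of 5%, 0.54 at 10% and 0.03 at 25%.
- P(declare effective) = Σ over x ≥ 3 of P(X₁ = x | n = 25) × P(X₂ ≥ 9 − x | n = 22). This gives 0.040 at 10% and 0.856 at 25%.

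The look is then reached whatever r is, and the stated 5% and 85% still hold. Power is 0.865 − 0.856 = 0.009 below the design with no look.

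**5. Sensitivity to the unstated denominator.** Suppose only the 25 qualifiers formed the denominator and every responder were a qualifier (both assumptions). A true overall rate of 10% would appear as 0.10 / 0.6 = 16.7% at r = 0.6, and P(stop) at the look would fall from 0.54 to 0.19.

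**The case against.** **The look may never come.** A reader might infer this from the wording. The documents do not support it as a prediction. It needs about 60% or fewer to reach 4 cycles, and nothing in them points to such a rate. The one available anchor, 0.81 from deaths alone, puts the 25th qualifier at about patient 31, with the look practically certain. At r = 0.7 the look is late but not lost.

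**Progressing patients can still count.** Sections 5.5, 5.7 and 10 let some patients continue after progression, and those who reach 4 cycles do qualify. Section 5.7 also lists progression without leukaemia as a reason for removal, while Section 10 allows continued treatment on conditions; these sections need reconciling. This narrows the point to patients who actually stop.

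**Early stoppers' outcomes are not always known.** A reader might assume every early stopper is a settled failure. The Section 10 response criteria require count changes to persist, and clinical benefit to be verified, over at least 8 weeks. The first scheduled on-treatment marrow is at the end of cycle 3. Some early stoppers will be unconfirmed or not assessable. This stands, and the trigger wording must say how they count.

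**The look analyses only selected patients.** A reader might infer this too. Section 12.1.2 uses the 25 only to time the look, and Section 14.2.2 requires everyone to be assessed, so early failures may already belong in the denominator. The gap is that it is unstated; the figures in step 5 are conditional.

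**Other safeguards exist.** There is a stop for "The early death of more than three of the first ten subjects, as defined by death within 28 days of beginning therapy", a Grade 4 toxicity rule, ad hoc board meetings, and a semiannual review that names efficacy. They cover part of the death and toxicity scenario. None is a futility rule, and the bar on assessing efficacy before the trigger conflicts with the semiannual review of efficacy.

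**Conclusion.** The concern holds as a matter of timing. On the text as written, patients who permanently stop in cycles 1 to 3 do not advance the only futility look, and nothing else brings it forward. For assumed completion of 80%, 70% and 60%, the trigger costs about 6, 11 and 17 patients beyond 25, before any overrun. Loss of the look becomes a material risk only at about 60% completion or lower: the probability that it occurs is 0.94 among 50 (0.86 among 47) at 60%, and 0.56 (0.39) at 50%.

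The consequence is bounded. The final 9-of-47 test is unaffected, and the worst case is treating the 47 to 50 patients already planned. The harm is avoidable exposure if the drug does not work. These sizes rest on the assumed r, on independence between patients, and on the literal reading of treatment for 4 cycles. A reading based on 4 cycles of follow-up would remove the problem, but it is not what the section says.

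**What to change.** Replace the trigger sentence in Section 12.1.2 with wording such as:

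> *Efficacy will first be assessed when each of the first 25 patients to start treatment has either received 4 cycles or permanently stopped treatment; all 25 form the denominator, and those who stopped without a response meeting the protocol criteria (including unconfirmed or not assessable) count as non-responders.*

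Keep the 10% rule and state it as a count: stop at 2 or fewer responders of 25. Add that the semiannual board review does not assess efficacy before this point, or say what it may do, so that the two statements agree.

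The cost is one or two sentences, with no new data or patients. Patients still on treatment keep their full 4 cycles before being judged. Stopping becomes slightly more frequent because early failures count, and power is about 1 percentage point below the design with no look (0.856 against 0.865). Two limits remain. Patients will still enter while the 25th completes or stops, so enrolment at the look will exceed 25 unless accrual is paused. The power figure also assumes that the 25 are all among the 47 in the final test, so the plan should say how any of them later found ineligible or unevaluable are handled.
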